## 1. PROTOCOL SUMMARY

### 1.1. Synopsis

**Protocol Title:** An open label single-centre, enabling study to investigate the optimum method for use of intradermal Substance P as a challenge agent in healthy participants

**Short Title:** Intradermal Substance P challenge in healthy participants

#### Rationale:

This study aims to establish a Substance P (SP) intradermal challenge model which will allow the future clinical evaluation of the pharmacological effects of antagonists to block or decrease the induced wheal and flare response.

#### Objectives and Endpoints:

##### Part 1

Objectives	Endpoints
Primary	

To characterise the wheal response over time following skin challenge with ascending concentrations of SP on a single day

	

Wheal response during the 2 h post-challenge period area under the curve (AUC) at each concentration of SP

Secondary	

To characterise the wheal response over time following skin challenge with ascending concentrations of SP on a single day

	

Wheal response during the 2 h post-challenge period at each concentration of SP (including maximum observed wheal response, time to maximum observed wheal response, time of complete wheal response disappearance)

Objectives	Endpoints

 
To characterise the flare response over time following skin challenge with ascending concentrations of SP on a single day
 
	
 
Flare response during the 2 h post-challenge period at each concentration of SP (including AUC, maximum observed flare response, time to maximum observed flare response, time of complete flare response disappearance)
 

 
To evaluate the safety and tolerability of SP
 
	
 
Incidence of Adverse Events (AE) and Serious Adverse Events (SAE)
 
Incidence of findings of clinical important changes in: 
 
vital signs
 
laboratory safety data
 
12-lead electrocardiogram (ECG)
 
 
 

## Part 2

Objectives	Endpoints
Primary	

 
To compare the wheal response over time following skin challenge with ascending concentrations of SP on 2 days
 
	
 
Wheal response during the 2 h post-challenge period (AUC) at each concentration of SP across 2 challenge days
 

Secondary	

 
To compare the wheal response over time following skin challenge with ascending concentrations of SP on 2 days
 
	
 
Wheal response during the 2 h post-challenge period at each concentration of SP across 2 challenge days (including maximum observed wheal response, time to maximum observed wheal response, time of complete wheal response disappearance)
 

Objectives	Endpoints

 
To compare the flare response over time following skin challenge with ascending concentrations of SP on 2 days
 
	
 
Flare response during the 2 h post-challenge period at each concentration of SP across 2 challenge days (including AUC, maximum observed flare response, time to maximum observed flare response, time of complete flare response disappearance)
 

 
To evaluate the safety and tolerability of SP
 
	
 
Incidence of Adverse Events (AE) and Serious Adverse Events (SAE)
 
Incidence of findings of clinical important changes in: 
 
vital signs
 
laboratory safety data
 
12-lead ECG
 
 
 

### Overall Design:

This is an open label single-centre, 2-part, prospective enabling study of SP intradermal challenge in healthy participants. Parts 1 and 2 will run sequentially. A schematic of the overall study design is provided in [Figure 1](#).

**Disclosure Statement:** This is a 2-part, single arm, sequential study with no masking.

### Number of Participants:

Part 1 will enrol a sufficient number of participants to achieve up to 12 participants who have completed the challenge visit. Once Part 1 is complete, SP concentrations to be given in Part 2 will be confirmed. Part 2 will occur only if Part 1 is successful.

Part 2 will enrol a sufficient number of participants to achieve up to 20 participants who have completed the 2 challenge visits. The study may be stopped after review of data from about the first 10 participants.

Participants who withdraw or are withdrawn from the study may be replaced. In Part 2, following screening, replacement participants must start at Challenge Visit 1.

Participants may be enrolled into Part 1 or Part 2, not both. Therefore, the anticipated sample size is up to 32 participants (not including replacements).

### Intervention Groups and Duration:

All participants will attend the clinical unit for a screening visit (V0) within 28 days before their first or only challenge visit.

**In Part 1**, participants will attend the unit as outpatients for 1 challenge visit. The duration of Part 1, including screening, is not expected to exceed 4 weeks for each participant.

[figure not shown]
**In Part 2**, participants will attend the unit as outpatients for 2 challenge visits and have 1 follow-up phone call; the timing of visits will be decided based on emerging data. The duration of Part 2, including screening and follow-up is not expected to exceed 7 weeks for each participant.

A schematic of each challenge day is provided in [Figure 2](#).

**Data Monitoring or Other Committee:** No

## 1.2. Schema

**Figure 1** Overall study design schematic

**Figure 2 Schematics of challenge days**

	Challenge Visit 1	Challenge Visit 2								
Part 1	• Wheal and flare post SP challenges (Panel A) only	Not applicable								
Part 2	• Wheal and flare post SP challenges (Panel A); and • IDM during SP challenges (Panel B)	• Wheal and flare post SP challenges (Panel A) • IDM during SP challenges (Panel B) • Biopsy post challenges (Panel C) • Before first and after last SP challenge: biomarker blood sample ^								
Panel A: Wheal and Flare measurement										

 
 Control challenge	Up to 2 h after challenge	SP challenge	
 
 Intradermal saline (negative) and histamine skin prick (positive)	Measurement of wheal response	Up to 2 h after challenge	
 
			Control challenge	Up to 2 h after challenge	SP challenge	Intradermal saline (negative) and histamine skin prick (positive)	Measurement of wheal response	Up to 2 h after challenge		
Control challenge	Up to 2 h after challenge	SP challenge								
Intradermal saline (negative) and histamine skin prick (positive)	Measurement of wheal response	Up to 2 h after challenge								

Acceptable negative and positive control responses* within 20 min after challenge, then start SP challenges
										

 
 At least 2 h before baseline sampling	Within 1 h before SP challenge	SP challenge	Up to 2 h after challenge	
 
 At the site of each SP injection (and saline control): placement of IDM tubing	At site of each SP injection (and saline control): pre-challenge IDM sample	Up to 4 intradermal injections of increasing SP concentrations	At site of each SP injection (and saline control): measurement of wheal and flare responses, and IDM sampling	
 
			At least 2 h before baseline sampling	Within 1 h before SP challenge	SP challenge	Up to 2 h after challenge	At the site of each SP injection (and saline control): placement of IDM tubing	At site of each SP injection (and saline control): pre-challenge IDM sample	Up to 4 intradermal injections of increasing SP concentrations	At site of each SP injection (and saline control): measurement of wheal and flare responses, and IDM sampling
At least 2 h before baseline sampling	Within 1 h before SP challenge	SP challenge	Up to 2 h after challenge							
At the site of each SP injection (and saline control): placement of IDM tubing	At site of each SP injection (and saline control): pre-challenge IDM sample	Up to 4 intradermal injections of increasing SP concentrations	At site of each SP injection (and saline control): measurement of wheal and flare responses, and IDM sampling							
Panel B: IDM measurement										

 
 At least 2 h before baseline sampling	Within 1 h before SP challenge	SP challenge	Up to 2 h after challenge	
 
 At the site of each SP injection (and saline control): placement of IDM tubing	At site of each SP injection (and saline control): pre-challenge IDM sample	Up to 4 intradermal injections of increasing SP concentrations	At site of each SP injection (and saline control): measurement of wheal and flare responses, and IDM sampling	
 
			At least 2 h before baseline sampling	Within 1 h before SP challenge	SP challenge	Up to 2 h after challenge	At the site of each SP injection (and saline control): placement of IDM tubing	At site of each SP injection (and saline control): pre-challenge IDM sample	Up to 4 intradermal injections of increasing SP concentrations	At site of each SP injection (and saline control): measurement of wheal and flare responses, and IDM sampling
At least 2 h before baseline sampling	Within 1 h before SP challenge	SP challenge	Up to 2 h after challenge							
At the site of each SP injection (and saline control): placement of IDM tubing	At site of each SP injection (and saline control): pre-challenge IDM sample	Up to 4 intradermal injections of increasing SP concentrations	At site of each SP injection (and saline control): measurement of wheal and flare responses, and IDM sampling							
Panel C: Biopsy sample										

 
 SP challenge	~20 min and ~1 h after challenge	
 
 2 intradermal injections of one of the SP concentrations	Skin biopsy at site of challenge Plus 1 control biopsy from non-challenged skin	
 
			SP challenge	~20 min and ~1 h after challenge	2 intradermal injections of one of the SP concentrations	Skin biopsy at site of challenge Plus 1 control biopsy from non-challenged skin				
SP challenge	~20 min and ~1 h after challenge									
2 intradermal injections of one of the SP concentrations	Skin biopsy at site of challenge Plus 1 control biopsy from non-challenged skin									

Abbreviations: IDM = intradermal microdialysis; SP = Substance P.

^ To coincide with safety laboratory blood sampling.

\* Acceptable saline and histamine responses are defined in the Study Reference Manual (SRM).

### 1.3. Schedule of Activities (SoA)

Protocol waivers or exemptions are not allowed. Therefore, adherence to the study design requirements, including those specified in the SOA, are essential and required for study conduct. This section lists the procedures and parameters of each planned study assessment. The exact timing of each assessment is listed in the SOA.

### 1.3.1. Screening

Visit (V)	V0	Notes
Procedure	Screening (up to 28 days before Day 1)	
Informed consent	X	
Inclusion and exclusion criteria	X	
Demography	X	
Complete physical examination including height and weight	X	
Medical /medication/drug/alcohol/tobacco history	X	Includes Substance usage and current medical condition
Drug/alcohol/cotinine test	X	As per standard local practice
HIV, Hepatitis B and C screening	X	If test otherwise performed within 3 months before first challenge day, testing at screening is not required.
Serum pregnancy test (WCBP only)	X	
FSH and estradiol (in WNCBP)	X	As required, if postmenopausal state in women is in doubt.
12-lead ECG	X	In triplicate. Mean of 3 measure used to confirm eligibility.
Vital signs	X	Blood pressure and heart rate, in triplicate. Mean of 3 measure used to confirm eligibility. Single measurement of temperature.
Control challenge (histamine/saline)	X	
Clinical chemistry/Haematology and urinalysis	X	
SAE review	X	From signing consent

Abbreviations: ECG = electrocardiogram; HIV = human immunodeficiency virus; SAE = serious adverse event; WCBP = women of childbearing potential; WNCBP = women of non childbearing potential.

### 1.3.2. Part 1 & Part 2 Challenge Visits

Visit (V)	V1, V2 (Part 2 only)					Follow-up phone call (5-7 days post last challenge day)	Early withdrawal	Notes
Procedure	Pre-challenge	Within 1 h before first control challenge	At least 20 min before first SP challenge	SP challenges	2 h after last SP challenge			
Clinical chemistry/Haematology and urinalysis		X			X*		X	*In Part 2, 2 h post last SP challenge at last challenge visit only.
12-lead ECG		X			X		X	Triuplicate measurements.
Vital signs		X			X		X	Refer to Section 8.2.2.
Brief PE		X						
Urine pregnancy test (WCBP only)	X							
Visual check of planned challenge sites	X							Prior to any other study procedures.
Saline and Histamine challenges			X					Histamine to be administered at least 20 cm from any IDM sampling
SP challenge				X				Part 1: Up to 4 SP injections: increasing concentrations of SP at a minimum of 20-min intervals. Part 2: Up to 10 SP injections: 

• up to 4 increasing concentrations of SP at a minimum of 20-min intervals, in duplicate

Visit (V)	V1, V2 (Part 2 only)					Follow-up phone call (5-7 days post last challenge day)	Early withdrawal	Notes
Procedure	Pre-challenge	Within 1 h before first control challenge	At least 20 min before first SP challenge	SP challenges	2 h after last SP challenge			
								
 
• a further 2 SP injections at one concentration may also be given, if ongoing data suggest biopsy samples are required
 

Wheal and flare assessment		See Section 1.3.3						
Blood sample for exploratory biomarkers		X			X			Part 2, V2 only.
IDM		See Section 1.3.3						Part 2 only
Skin punch biopsy		See Section 1.3.3						Part 2, V2 only. May or may not be performed based on ongoing data.
AE review		<===== =====>					X	
SAE review		<===== =====>					X	
Concomitant medication review		X						Review of medications since last visit, if applicable.
Follow-up on possible reactions at sites of IDM/biopsy						X		Part 2 only.

Abbreviations: AE = adverse event; ECG = electrocardiogram; IDM = intradermal microdialysis; SAE = serious adverse event; SP = substance P.

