### 1.3.3. Each challenge

Procedure	Min in relation to time of each intradermal injection of each SP or saline, or the time of skin prick administration of histamine											Notes
	Pre-challenge	0	5	10	15	20	30	40	60	90	120	
Challenge		X										
Wheal and flare assessment			X	X	X	X		X	X	X	X	See Section 8.5.2 for methods.
IDM (SP and saline challenged sites, as indicated in Figure 2)	X	←-----→										Part 2 only (see Figure 2). Tubing inserted at least 2 h before baseline sampling. A 30-min pre-challenge sample will be taken within 1 h before challenge. Post-challenge samples will be collected in 10-min interval from 0–120 min post-challenge.
Skin punch biopsy						X				X		Part 2, Challenge Visit 2 only (see Figure 2). 20-min and 60-min samples to be taken from different SP challenged sites; a third biopsy to be taken from a non-challenged area of skin to be collected at approximately the same time as the 20-min SP biopsy. Biopsy sampling may or may not be included in the Part 2 based on ongoing data.

Abbreviations: IDM = intradermal microdialysis; SP = substance P.

- The timing and number of planned study assessments, including the challenge or sampling and assessment time points in Part 2 (safety, wheal and flare, biomarker samples [including IDM and skin punch biopsy]) may be altered during the course of the study based on newly available data.
- Any changes to the timing or addition of time points for any planned study assessments in Part 2 as the result of emerging data from Part 1 of this study must be documented and approved by the relevant study team member and then archived in the sponsor and site study files but will not constitute a protocol amendment. The Competent Authority (CA) and ethics committee (EC) will be informed of any safety issues that constitute a substantial amendment and require alteration of the safety monitoring scheme or amendment of the informed consent form (ICF). The changes will be approved by the EC before implementation.
- Acceptable time windows around the nominal time points for specific assessments will be included in the Study Reference Manual (SRM) and assessments performed within these time windows will not constitute a protocol deviation.

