Histamine intradermal challenge	
Highly sensitised patients may experience stronger local reactions. In extremely rare cases generalised side reactions and even severe systemic reactions (anaphylactic shock) may occur.
 
Mild systemic adverse reactions include rhinitis, conjunctivitis, asthma, generalized exanthema, or urticaria. More severe adverse reactions include itching of tongue, throat, palms or soles. The reaction may progress to cyanosis, tachycardia, dizziness, headache, bronchial constriction, urticaria, asthma, marked hypotension or hypertension, vomiting, urination or defecation.
	
Histamine challenge is an established proinflammation/allergy test.
 
Only small concentrations will be administered via skin prick. One drop (~50 µL) of 1.7 mg/mL solution is applied to the skin and a prick needle is passed through to introduce a small amount intradermally. This dose and technique are commonly used in histamine skin challenge test. The participants will be closely monitored during administration of histamine challenge. The clinical site will have appropriate precautions and treatments in place, per the product label, during administration and post-administration observation.

Potential Risk of Clinical Significance	Summary of Data/Rationale for Risk	Mitigation Strategy
Study Procedures		
Intradermal Microdialysis	Mild pain, bruising and irritation at dialysis site	Site staff under supervision of experienced staff will follow local standard approaches to perform the procedure.
Phlebotomy	Fainting, mild pain, bruising, irritation or redness at a phlebotomy site may be associated with blood draws.	Experienced site staff will follow local standard approaches for managing events related to blood draws.  Participants are instructed to visually inspect phlebotomy sites after clinical visit are informed what signs of inflammation/infection to watch for and contact the investigator with any concerns.

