Skin Biopsy	
Complications of punch skin biopsy are uncommon but may include bleeding, infection, and scarring.
 
Scarring risk is increased in individuals with a history of scarring and in individuals with darker skin.
	
Exclusion criterion #3: History of risk for or actual experience of complications from skin biopsy including excess bleeding, infection, or scarring/keloid formation (Participants with darker skin (Fitzpatrick>2) will be excluded).
 
Observation of the subject while in the clinical unit and at follow-up after discharge from the unit.

Potential Risk of Clinical Significance	Summary of Data/Rationale for Risk	Mitigation Strategy
		Participants are instructed to visually inspect skin biopsy sites after clinical visit and are informed what signs of inflammation/infection to watch for and contact the investigator with any concerns.

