**At each challenge visit, up to 4 concentrations of SP will be assessed, as follows:**

- In Parts 1 and 2:
  - Participants will first receive saline, by intradermal injection, and histamine by skin prick, as negative and positive controls.
  - If the wheal responses within the 20 min after each control challenge do not meet the acceptable saline and histamine responses (as defined in the SRM), the participant will not receive SP.
    - If it happens in Part 1 or on Challenge Visit 1 in Part 2, the participant will be withdrawn from the study.
    - If it happens on Challenge Visit 2 in Part 2 and if the participant marginally fails to meet the control criteria (as defined in the SRM), they may have the tests repeated. If they still fail to meet the control criteria, they will be withdrawn from the study.
  - Following confirmation of acceptable control responses, participants will receive up to 4 intradermal injections of SP at different concentrations; injections will be given sequentially from lowest to highest concentration; wheal and flare responses will be assessed after each challenge.

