## **7.2. Discontinuation of Study Intervention**

In rare instances, it may be necessary for a participant to permanently discontinue study intervention. If study intervention is permanently discontinued, the participant will remain in the study until the end of that challenge visit to be evaluated for safety. See the SoA for data to be collected at the time of discontinuation of study intervention and follow-up and for any further evaluations that need to be completed.

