## **7.3. Participant Discontinuation/Withdrawal from the Study**

- A participant may withdraw from the study at any time at his/her own request or may be withdrawn at any time at the discretion of the investigator for safety, behavioural, compliance or administrative reasons. This is expected to be uncommon.
- At the time of study discontinuation, the participant should undergo the assessments for early withdrawal shown in the SoA.
- The participant will be permanently discontinued both from the study intervention and from the study at that time.
- If the participant withdraws consent for disclosure of future information, the sponsor may retain and continue to use any data collected before such a withdrawal of consent.
- If a participant withdraws from the study, he/she may request destruction of any samples taken and not tested, and the investigator must document this in the site study records.

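### The check on microdialysis and biopsy sites is scheduled only at the follow-up call, so a Part 2 participant who withdraws early has no clearly scheduled site follow-up

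*Protocol*

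**What the plan says.** The Schedule of Activities in Protocol Section 1.3.2 has a Part 2 row titled "Follow-up on possible reactions at sites of IDM/biopsy". It carries one mark, in the column for the phone call 5 to 7 days after the last challenge day. The early-withdrawal cell is empty, although that column is used for laboratory tests, ECG, vital signs, AE review and SAE review.

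On withdrawal, Section 7.3 says: "At the time of study discontinuation, the participant should undergo the assessments for early withdrawal shown in the SoA". It then says: "The participant will be permanently discontinued both from the study intervention and from the study at that time". For a participant who stops only the intervention, Section 7.2 keeps them to the end of that challenge visit and refers back: "See the SoA for data to be collected at the time of discontinuation of study intervention and follow-up".

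Section 4.1 sets out one route to same-day withdrawal, failure of the saline and histamine control criteria: "If it happens in Part 1 or on Challenge Visit 1 in Part 2, the participant will be withdrawn from the study". On probe timing, Section 1.3.3 says: "Tubing inserted at least 2 h before baseline sampling. A 30-min pre-challenge sample will be taken within 1 h before challenge".

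The risk table in Section 2.3.1 treats the two procedures differently. The skin biopsy row names "Observation of the subject while in the clinical unit and at follow-up after discharge from the unit" and also tells participants to inspect their sites and contact the investigator. The only mitigation in the microdialysis row is "Site staff under supervision of experienced staff will follow local standard approaches to perform the procedure".

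**The concern.** The sponsor judged that probe and biopsy sites merit a check some days later. That need arises from the procedure, yet the schedule attaches the check to a contact that only participants who stay in the study are clearly due to receive.

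A reaction that appears after a withdrawn participant has left the unit, with no AE reported by then, has no scheduled contact at which it would be found. These are healthy volunteers for whom Section 2.3.2 states there is no benefit. A biopsied participant at least has an instruction to self-inspect and make contact; the microdialysis row of the risk table contains none.

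Nothing in the statistical results is at stake. Section 8.3.1 closes AE collection 2 h after the last SP challenge, so the call falls outside that window for completers too.

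**Working it through.** There is no planned figure to reproduce. The check consists of reading the sections against each other, followed by short arithmetic on timing and on numbers of sites.

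**1. The schedule row.** Marked cells in the site-reaction row: 1 (the call). Marked cells for that row under early withdrawal: 0. Rows marked under early withdrawal: 5 (laboratory tests, ECG, vital signs, AE review, SAE review). None is specific to probe or biopsy sites.

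**2. The withdrawal rule.** Section 7.3 sends the withdrawn participant to that column and discontinues them from the study at that time. Section 4.4 counts the call among the phases that a completer has finished. No section says that the call survives withdrawal. Section 7.2 points back to the schedule, so it does not settle the question.

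**3. Can probes be in place when a participant is withdrawn for failed controls?** Inputs: at least 120 min from tubing to baseline sampling and a 30-min baseline sample (Section 1.3.3); at least 20 min from controls to first SP (Section 1.3.2); controls read within 20 min (Section 4.1).

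- Tubing to that site's challenge: 120 + 30 = 150 min at least.
- If the first SP injection at a probe site follows the controls by the minimum 20 min (an assumption), tubing precedes the controls by at least 150 − 20 = 130 min.
- For tubing to wait until after the 20-min control reading, the gap from controls to the first probe-site injection must be at least 20 + 150 = 170 min.

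The protocol sets no maximum gap, so the order is an inference. Two details support it: Figure 2 (Panel B) also places tubing at the saline control site, and the control row of the schedule requires histamine to be kept at least 20 cm from any microdialysis sampling.

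**4. Who is exposed.**

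| Situation (Part 2) | Sites without a scheduled later check |
|---|---|
| Failed controls at Visit 1, probes already in | Probe sites of that visit |
| Other withdrawal at or within days after Visit 1 | Probe sites of that visit, apart from whatever the general AE review at withdrawal picks up |
| Failed controls at Visit 2 | Only probes placed that day; earlier sites are covered by that day's brief examination, which includes skin, and by the AE review |
| Withdrawal after biopsy at Visit 2, before the call | Probe and biopsy sites of that visit |

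Probe sites per visit: 4 SP + 1 saline = up to 5. Biopsy sites: 2 challenged + 1 unchallenged = up to 3, at Visit 2 only and only if biopsies are done.

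**5. Is it a contradiction or a gap?** For biopsy, the risk table names follow-up after discharge, and the schedule with Section 7.3 does not provide it for a withdrawn participant; those texts conflict. For microdialysis the risk table promises no follow-up, so the shortfall is only against the schedule's own row.

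**The case against.** The strongest reply is that a blank early-withdrawal cell does not cancel the call. The call is a separate column, timed from the last challenge day and restricted only to Part 2, and a withdrawn participant still has a last challenge day. Section 7.2, read to its end, also refers the site to the schedule for further evaluations, and the biopsy row of the risk table makes no exception for withdrawn participants. On this reading the protocol is incompletely cross-referenced, and a site could properly make the call.

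That shows the text is ambiguous. It does not show that the call is required: nothing forbids it after withdrawal, but nothing asks for it, and Section 7.3 points the other way.

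Other points limit the weight of the concern, and they stand:

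- AE and SAE review is marked at early withdrawal, so a reaction already present is captured. On same-day withdrawal that review comes too early to find a delayed one.
- Under Section 8.3, the investigator keeps responsibility for AEs that are serious, related or the cause of discontinuation. This covers events already reported.
- The biopsy case is narrow. Failed controls mean no SP, so that route cannot lead to biopsies of SP-challenged sites. What remains is withdrawal between biopsy and call.
- All participants passed a control test at screening, which makes failure at Visit 1 less likely.
- The listed microdialysis risks are mild. The participant leaflet, which is not available here, may contain self-inspection advice, so the silence of that risk row should carry little weight.

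**Conclusion.** The concern holds, as a minor point. Followed as written, the schedule and Section 7.3 leave a Part 2 participant who is withdrawn on the day of a probe insertion or biopsy, or within days of it, with no clearly scheduled post-discharge site check. The reading of the schedule row and of Section 7.3 rests on no assumption.

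The clearest case, failed controls at Visit 1 with probes already in place, does rest on one: that the gap from controls to the first probe-site injection is under 170 min. At the 20-min minimum, probes are in at least 130 min before the controls. Withdrawal for any other reason after probes are in does not need this assumption.

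The size is up to 5 probe sites per visit and up to 3 biopsy sites per affected participant. How many participants would be affected cannot be derived from the documents. No effect on the primary or planned safety analyses is claimed.

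**What to change.** Add a note to the existing site-reaction row in Section 1.3.2, and a matching sentence in Section 7.3: every Part 2 participant who has had a probe inserted or a biopsy taken receives the existing call 5 to 7 days after their last such procedure, whether or not they have been withdrawn, unless they decline contact.

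The cost is one note, one sentence, and one phone call of the existing type per affected participant. No visit, procedure or analysis is added.
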